4.6.1 Imputation Rules for AE Onset Date and Medication Start Date

If the start date (AE onset date, medication start date) is partially missing or completely missing, the following rules will be applied:

- If the start date is completely missing, then the start date will be imputed as the reference start date.
- Partial start date where only the year is known:
 - The start date will be imputed as the reference start date if the year of start date is the same as the year of the reference start date; otherwise, day and month of start date will be imputed as the first day of the year (i.e., 01 January).
- Partial start date where only the month and year are known:
 - The start date will be imputed as the reference start date if the year and month of start date are the same as year and month of the reference start date; otherwise, day of start date will be imputed as the first day of the month.
- If the imputed start date is after the stop/end date, the start date will be imputed as the stop/end date.

4.6.2 Imputation Rules for AE End Date and Medication End Date

If the end date (AE end date, medication end date) is partially missing or completely missing, the following rules will be applied:

- If the end date is completely missing and not ongoing, then the end date will be imputed as the last study participation date.
- Partial end date where only the year is known:
 - The end date will be imputed as the last study participation date if the year of end date is the same as the year of the last study participation date; otherwise, day and month of end date will be imputed as the last day of the year (i.e., 31 December).
- Partial end date where only the month and year are known:
 - The end date will be imputed as the last study participation date if the year and month of end date are the same as year and month of the last study participation date; otherwise, day of end date will be imputed as the last day of the month.
- Imputed stop dates must be on or after the start date.

4.6.3 Missing Severity Assessment for Adverse Events

If the severity is missing for an AE starting on or after the reference start date, then a severity of “Severe” will be assigned. The imputed values for severity assessment will be used for table summaries, while the actual values will be presented in data listings.

4.6.4 Missing Relationship to Study Drug for Adverse Events

If the relationship to study drug is missing for an AE starting on or after the reference start date, a causality of “Definitely Related” to the study drug will be assigned. The imputed values for relationship to study drug will be used for table summaries, while the actual values will be presented in data listings.

4.6.5 Missing Data Imputations for Sensitivity Analyses of Primary Efficacy Endpoint

The missing values for GA area measurement will be imputed in the following two steps.

Step 1, impute the intermediate missing data to achieve the monotone missing pattern.

The missing value(s) between two visits with measured GA area will be imputed by Markov-Chain Monte-Carlo (MCMC) method, which was proposed by Li (1988) and Liu (1993), to achieve the monotone missing pattern (i.e., where a missing GA area measurement at a visit for a subject implies that GA area measurements at all subsequent visits for that subject are missing). The MCMC model will include treatment arm, the GA area measurements at baseline, Month 6, Month 12, Month 18, and Month 24. This MCMC method will use a seed of 20193001 and a total of 100 imputations are done in the MCMC step.

Step 2, impute the monotone missing data generated in Step 1 using Pattern Mixture Model Method (a copy-reference approach) and Tipping Point Analysis Method (a delta-adjusted approach), respectively.

- Pattern Mixture Model Method (a copy-reference approach):
 - Subjects with monotone missing data in the placebo arm will have missing data imputed based on the observed values in the placebo arm.
 - Subjects in the ALK-001 arm with monotone missing data who did not discontinue treatment or withdraw from the study due to reasons that are potentially related to study drug or lack of efficacy will have missing data imputed based on the observed values in the ALK-001 arm.
 - Subjects in the ALK-001 arm with monotone missing data who discontinued treatment or withdrew from the study due to reasons that are potentially related to study drug or lack of efficacy will have missing data imputed based on placebo arm.
- Tipping Point Analysis Method (a delta-adjusted approach): the tipping point analysis method will be implemented for the ALK-001 arm under the missing not at random (MNAR) assumption by searching for a tipping point that reverses the conclusion regarding positive treatment effect.

- Subjects with monotone missing data in the placebo arm will have missing data imputed based on the observed values in the placebo arm.
- Subjects in the ALK-001 arm with monotone missing data without treatment discontinuation or early withdrawal by subject will have missing data imputed based on the observed values in the ALK-001 arm.
- Subjects in the ALK-001 arm with monotone missing data due to treatment discontinuation or early withdrawal by subject will have missing data imputed based on the available values in the ALK-001 arm (observed values plus values imputed for intermediate missing data) with a shift parameter added to the imputed values.
- Multiple imputation will be implemented with the shift parameter. The shift parameter will be allocated to the missing data point(s) proportionally across timepoints. The precision of the tipping point will be at two decimal points. A tipping point may not exist within reasonable clinical assumptions.

The following three standard step process will be followed to generate inference from the imputed data:

1. Imputation step: the missing data are filled in 100 times to generate 100 complete datasets by either the pattern mixture model method or the tipping point analysis method.
2. Analysis step: the 100 complete datasets are analyzed by using the same approach as for the analysis for the primary objective.
3. Pooling step: the results from the 100 complete datasets are combined for the inference.

4.6.6 Handling of Incorrect MNRead Data

We utilized the MNRead iPad application (app) to improve the testing process for technicians and subjects. Upon test completion, the app automatically computes MNRead parameters. These parameters are then written down on the source documents and entered in the MNRead Case Report Form (CRF) of the Electronic Data Capture (EDC) system. Parameters may also be exported in raw format (CSV) and as an image (JPG) via email.

- **Errors in MNRead Parameters**

The MNRead app generally provides accurate parameter calculations. However, during blind review, it was found that the app could compute inaccurate parameters, for example in cases where a technician failed to press the "cannot read" button when a subject is unable to see very small letters. This results in incorrect parameters, which should be corrected prior to analysis.

- **Correction of Inaccurate Data**

To prevent use of erroneous data in the analysis, and prior to database lock (DBL), CSV files received by sponsor prior to DBL will be manually reviewed, marked for errors, and corrected, typically by removing spurious data points. In cases where a CSV file is

unavailable, the data may be re-created from the JPG chart to create a CSV file, if possible. In cases where neither CSV nor JPG files are available, the EDC data will be reviewed and spurious data will be removed.

- **Parameter Calculation Methods**

MNRead parameters will be calculated using one of the following methods:

- Manual calculation, similar to traditional paper-based MNRead charts
- Computer algorithms, such as those provided by the mnreadR package (available at <https://cran.r-project.org/web/packages/mnreadR/index.html>)

These steps ensure that the MNRead parameters used in the study are accurate and reliable, maintaining the integrity of the data analysis.

4.7. Derived Variables and Parameters

Variables requiring calculation will be derived using the following formulas:

- Duration of study (month) = (last study participation date – informed consent date +1)/ 30.4375
- Duration of exposure (day) = last treatment date – reference start date +1
- Duration of exposure (month) = duration of exposure (day)/30.4375
- Percentage of duration of exposure (%) is calculated as [total number of days with no lapse in treatment (day)]/ [duration of exposure (day)] x 100.
- Change from baseline = postbaseline value – baseline value
- Percentage change from baseline = ([postbaseline value – baseline value] / baseline value) x 100
- Low Luminance Deficit (LLD) = one eye's Best Corrected Visual Acuity (BCVA) score – Low Luminance Visual Acuity (LLVA) score

5.0. STUDY SUBJECTS

5.1. Subject Disposition

Subject disposition will be summarized for all screened subjects and will include the number of subjects screened, screen failure, randomized, the number and percent of subjects in each analysis set (ITT, FAS, PP, Safety), who have completed and who have prematurely discontinued the study, primary reason for discontinuation (investigator's decision, unmasking, non-compliance, adverse events-related, subject's decision, sponsor's decision, lost to follow-up, death, other).

A flowchart will also be provided with the count of subjects screened, randomized, and who completed the study.

A listing will be provided for all subjects with additional details on the reason for not completing the study, which analysis sets they were in, and reason for excluding from the PP population, if applicable. A listing of screen failure subjects will also be presented.

5.2. Protocol Deviations

Protocol deviations deemed important by Sponsor will be summarized by category (safety, informed consent, eligibility, protocol implementation, and other) and subcategory within category for the ITT Set.

All protocol deviations, including individual subjects when applicable, will be listed.

5.3. Demographic and Baseline Characteristics

Collected demographic and baseline characteristics, including, for example, age at enrollment, sex, race, ethnicity, body weight, height, BMI, age of onset of GA, age of onset of AMD, presence of GA, status of FAF GA in terms of focus/delineation and location within frame, GA foveal status, GA distance to fovea, presence of peripapillary atrophy and contiguity status with GA, GA lesion multifocality status, number of GA lesions, total GA lesion area (mm²) (FAF), GA FAF junctional zone type and pattern, presence of AMD, presence of intermediate AMD, presence of reticular pseudodrusen(s) (RPD), presence of drusen, presence of large drusen, presence of CNV location and CNV classification, presence of elevated blocked fluorescence on fluorescein angiography (FA), presence of window defect on FA, presence of vascular filling defect on FA, presence of staining on FA, presence of leakage on FA, presence of CNV on FA, presence of chorioretinitis using multi-modal assessment, maximum reading speed by MNRead, reading accessibility index by MNRead, critical print size by MNRead, reading acuity by MNRead, reading speed by IReST, BCVA score, LLVA score, LLD score, FRI index score, TTO, VFQ-25 total score, CNV in the fellow eye collected at baseline, will be summarized by treatment arm for the ITT Set and Safety Set respectively.

A listing of all subjects in the ITT Set with some of their key characteristics will be provided, including for example age at enrollment, age of onset, sex, baseline area of atrophy, visual acuity at baseline.

5.4. Medical History

Medical history will be coded using the Medical Dictionary for Regulatory Activities (MedDRA) dictionary version 22.0 or higher following MedDRA Term Selection Points to Consider.

Medical history will be summarized by system organ class and preferred term by treatment arm for the ITT Set.

A listing of medical history (ocular/non-ocular) for all subjects will be provided, including information on body system, condition/illness/procedure, start and end date, and whether it was ongoing at screening.

5.5. Prior and Concomitant Medications

Prior and concomitant medications will be coded using World Health Organization (WHO) Drug Dictionary Version September 2023.

Prior medications will be defined as those medications started and ended prior to the reference start date. Concomitant medications will be defined as those medications started on or after the reference start date, or started prior to and continued after the reference start date.

Concomitant medications will be tabulated by Anatomical Therapeutic Chemical (ATC) level 2 and preferred name for the Safety Set. A subject with multiple medications taken within the same ATC level 2 and/or preferred name will be counted only once for that level of summarization.

A listing of concomitant medications for all subjects will be provided, including information on medication/supplement/therapy, indication, dosing information, start and end date, and whether it was taken before or after the reference start date.

6.0. EFFICACY ANALYSIS

Efficacy analysis including primary, key secondary, secondary, and exploratory analysis will be performed primarily using the Full Analysis Set (FAS), with subjects grouped according to the treatment assigned at randomization. Available data from all randomized subjects regardless of adherence to the protocol will be included in the efficacy analyses; this includes data from subjects who discontinued study drug early but continued with study assessments.

Unless otherwise noted, hypothesis testing and estimation of treatment effects will be performed with a mixed effect model that includes data from two treatment arms: ALK-001 and Placebo. All hypothesis tests for efficacy endpoints will be two-sided.

6.1. Analyses of Primary Efficacy Endpoint

An Eligible Eye is defined as an eye with (a) measurable GA and (b) no presence of CNV at baseline as determined centrally by a central reading center according to combined review of optical coherence tomography (OCT) and color fundus photograph (CFP) (“Multimodal imaging”), and FA. GA lesion size will be measured independently by three readers on FAF imaging. The final GA lesion size (area) for each subject’s Eligible Eye, adjudicated from the assessments by three readers, will be used in the analysis.

The primary efficacy endpoint is the mean rate of growth (slope) in the GA area as measured by FAF from baseline to Month 24.

6.1.1 Estimand

The following attributes define the estimand for primary endpoint evaluation:

- A. **Treatment:** ALK-001 14 mg versus placebo, taken once a day
- B. **Population:** GA subjects defined by inclusion and exclusion criteria in FAS
- C. **Variable (or endpoint):** growth rate (slope) of the GA area over 24 months

D. Population-level summary: difference in the mean rate of growth (slope) of the total GA area over 24 months between ALK-001 14 mg versus placebo according to the linear mixed-effects model (LMM).

E. Intercurrent events (ICEs) and strategies for addressing ICEs:

- a. *Treatment changes* (such as interruptions or lapses, non-adherence, dose changes, discontinuation, use of additional therapy due for example to development of CNV): “treatment policy strategy” – i.e., treatment changes will be ignored and all data collected will contribute to the analysis.
- b. *Lost to follow-up or withdrawal*: “while on treatment strategy” – i.e., all data collected up to the date a patient has been lost to follow-up or withdrawal will contribute to the analysis.
- c. *COVID-19*: “treatment policy strategy” - i.e., impact of COVID-19 pandemic will be ignored and all data collected will contribute to the analysis.
- d. *Cataract surgery*: “while on treatment strategy” – i.e., if a patient has cataract surgery in an eye with GA, data collected on that eye up to the time of cataract surgery + 3 months will contribute to the analysis.

These ICEs will be handled with a treatment policy strategy whereby any measured value will be used as is. Missing data resulting from these intercurrent events will be handled implicitly within the linear mixed-effects model analysis that assumes missing at random (MAR).

6.1.2 Hypothesis Testing

The null (H_{1a}) and alternative (H_{1b}) hypotheses for the primary efficacy endpoint are the following:

- H_{1a} : There is no difference between ALK-001 and Placebo in mean growth rate (slope) of the GA area over 24 months based on FAF for the Full Analysis Set.
- H_{1b} : There is difference between ALK-001 and Placebo in mean growth rate (slope) of the GA area over 24 months based on FAF for the Full Analysis Set.

The hypothesis test for the primary endpoint will be based on a two-sided alpha level of 0.05 and the study will be considered positive if the null hypothesis (H_{1a}) is rejected favoring ALK-001.

6.1.3 Main Analysis of Primary Efficacy Endpoint

The mean rates of change (slope) in the GA area will be computed for the ALK-001 and the placebo arms, by use of a linear mixed-effects model applied to the GA area measured on FAF images at time points (baseline, Month 6, Month 12, Month 18 and Month 24) assuming time as continuous and linear (“slope model”).

The analysis model will use the change from baseline in the GA area measured by FAF as the response variable, and will include treatment arm (ALK-001, placebo), pattern of FAF at the junctional zone of GA (banded/diffuse, focal/other/cannot grade), GA lesion multifocality (multifocal, unifocal/other/cannot grade) and foveal status (foveal sparing, subfoveal/cannot grade) as fixed effects, baseline GA lesion area and time (year, continuous assuming linearity) as

covariates, time \times treatment interaction, and baseline GA lesion area \times time interaction. Random effects include subject and subject's eye (OD or OS). A common unstructured covariance matrix will be used to model the within-subject errors, and the Kenward-Roger's (Kenward and Roger 1997) method will be used to estimate denominator degrees of freedom. If the model fails to converge, alternative structures (heterogenous autoregressive (1), heterogeneous compound symmetry, autoregressive (1), or compound symmetry, in this order) will be considered.

The mean rate of change (mm^2/year), standard error, and 95% confidence interval (CI) will be estimated from baseline to Month 24 for each treatment arm. The estimated difference in slopes among the treatment groups along with the 95% CIs and p-value will be provided to test the significance of the treatment effect.

The observed values for the GA area (mm^2) of Eligible Eyes will be summarized by treatment group and visit. Summaries will present the descriptive statistics for baseline, absolute values and change from baseline data.

The mean change from baseline \pm the standard error in the GA area (mm^2) of Eligible Eyes as well as the Least-Squares (LS) mean of the change from baseline \pm the standard error in GA area (mm^2) of Eligible Eyes will be plotted over time by treatment group.

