3.2. Sample Size

The initial sample size was based on literature data on the progression of GA at the time the study was started. With 300 subjects and assuming that 80% of subjects are evaluable for the primary outcome measure, the study has an 80% power to detect, after 24 months of treatment, a 33% slowing in GA growth rate with a 2-tailed significance of 0.05, assuming a conservative standard deviation of 1.5 mm²/year and an average GA growth rate of 1.8 mm²/year in the control group.

Based upon natural history literature data updated as of the date of this SAP, and the area of GA, indicating an average GA growth rate of 1.8 mm²/year with a standard deviation of 1.2 mm²/year, with 200 subjects and considering that 80% of subjects completed the study and are expected to

have evaluable data for the primary outcome measure, the study has an 80% power to detect, after 24 months of treatment, a 33% slowing in GA growth rate with a 2-tailed significance of 0.05.

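### SAP 6.1.3: the primary slope model has no random slope and allows AR(1) and compound symmetry as fallbacks; if either is used, type I error is well above 5%

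*SAP*

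**What the plan says.** SAP 6.1.3 describes a linear mixed model "applied to the GA area measured on FAF images at time points (baseline, Month 6, Month 12, Month 18 and Month 24"), with time continuous and linear. The response comes next: "The analysis model will use the change from baseline in the GA area measured by FAF as the response variable". For the arm slopes, "95% confidence interval (CI) will be estimated from baseline to Month 24 for each treatment arm".

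The random effects are subject and the subject's "eye (OD or OS). A common unstructured covariance matrix will be used to model the within-subject errors". If the model does not converge, "alternative structures (heterogenous autoregressive (1), heterogeneous compound symmetry, autoregressive (1), or compound symmetry, in this order) will be considered". No random slope on time is mentioned.

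Other sections bear on this:

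- SAP 4.7 defines change as a post-baseline value minus the baseline value.
- SAP 4.1 and 6.1 admit every Eligible Eye, so one subject can contribute two.
- SAP 3.2 bases power on a mean growth rate of 1.8 mm²/year "with a standard deviation of 1.2" mm²/year, "with 200 subjects and considering that 80% of subjects completed the study".
- Under SAP 6.1.2, "the study will be considered positive if the null hypothesis" of equal slopes is rejected in favour of ALK-001. SAP 6.2.1 opens the LLVA and BCVA tests only after that.

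**The concern.** Eyes grow at different rates, so change from baseline fans out over time. With a growth-rate SD of 1.2, its variance is about 1.44t²: 0.36 mm⁴ at Month 6 (1.44 × 0.25) and 5.76 mm⁴ at Month 24 (1.44 × 4). AR(1) and CS force one variance on every visit, and a random intercept adds only a constant. Without a random slope, these models treat differences in growth rate between eyes as visit-level noise that averages out over visits. The standard error of the slope difference is then too small. Unstructured, heterogeneous AR(1) (ARH(1)) and heterogeneous CS (CSH) can follow the fanning, so what matters is whether the fallback goes past them.

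That is linked to an open point in 6.1.3. Change from baseline is zero for every eye at baseline, and the section does not say whether those rows are response records. If they are, the baseline variance is zero and the first three structures have no finite likelihood maximum.

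A third issue arises with two eyes. If the growth rates of a subject's eyes are correlated, a subject random intercept does not carry that correlation into the slopes.

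At stake is the p-value of the only primary test, which also gates both key secondary endpoints.

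**Working it through.** **1. The plan's power figure.** With 160 evaluable subjects at 2:1 and a difference of 0.33 × 1.8 = 0.594, the standard error is 1.2 × √(1/106.7 + 1/53.3) = 0.2013. Power is Φ(0.594/0.2013 − 1.96) = Φ(0.99) = 83.9%, against the stated 80%. The mismatch is conservative and does not bear on this point.

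**2. Set-up.** From SAP 3.2: slope SD 1.2 (variance 1.44) and 160 subjects, taken as 107:53, so 1/107 + 1/53 = 0.02821. Assumed, not in the documents: one eye per subject, linear growth, and measurement SD s = 0.1, 0.3 or 0.5 mm².

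**3. Compound symmetry.** With complete data the slope estimate is the within-eye least-squares slope. Let m be the number of visits and Sxx = Σ(t − mean t)².

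- True variance per subject: 1.44 + s²/Sxx.
- Residual variance the model settles on: [160(1.44·Sxx + (m−1)s²) − 2(1.44·Sxx + s²)] / [160(m−1) − 2].
- Model variance per subject: that residual divided by Sxx.
- Type I error: 2[1 − Φ(1.96 × model SE / true SE)].

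Months 6–24, s = 0.3: m = 4 and Sxx = 1.25. The true SE is √(1.512 × 0.02821) = 0.2065. The residual is (331.2 − 3.78)/478 = 0.685, so the model SE is √(0.685/1.25 × 0.02821) = 0.1243. The ratio is 0.602 and type I error is 23.8%.

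Baseline rows kept, s = 0.3: m = 5 and Sxx = 2.5. The shared baseline error cancels within an eye, so the same formulas apply. The true SE is √(1.476 × 0.02821) = 0.2041. The residual is (633.6 − 7.38)/638 = 0.9815, so the model SE is 0.1052. The ratio is 0.516 and type I error is 31.2%.

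**4. All settings.** AR(1) has no such closed form. Its limiting REML fit was found numerically and the same type I formula applied. Figures in brackets are simulated REML fits, 3,000–4,000 null trials per s.

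| Covariance and rows | s = 0.1 | s = 0.3 | s = 0.5 |
|---|---|---|---|
| CS, Months 6–24 | 25.7% (25.1) | 23.8% (24.2) | 20.8% (20.8) |
| AR(1), Months 6–24 | 26.2% (25.6) | 19.6% (19.9) | 12.6% (12.8) |
| CS, baseline rows kept | 32.7% (32.0) | 31.2% (31.4) | 28.6% (28.8) |
| AR(1), baseline rows kept | 34.0% (33.4) | 27.2% (27.9) | 19.3% (20.1) |

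Only rejections favouring ALK-001 make the study positive. Halving the ranges gives about 6–13% and 10–17%, against 2.5%.

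**5. Structures tried before AR(1) and CS, one eye, Months 6–24.** Unstructured: 6.1% in 423 simulated trials (Monte Carlo SE about 1.1 points), compatible with 5%. ARH(1) and CSH with a random intercept: 5.1–6.5%.

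**6. Zero rows kept.** As the baseline variance falls from 1 to 10⁻¹⁰, minus the REML log-likelihood falls from −25 to −1801 (unstructured), 310 to −1465 (ARH(1)) and 386 to −1393 (CSH), with no floor. AR(1) and CS do have finite optima.

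**7. Two eyes, AR(1) or CS.** With 30–100% of subjects bilateral, slope correlation 0.3–0.9 and s = 0.3 (all assumed), type I error is about 23–39% with Months 6–24 only and 30–47% with baseline rows kept.

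**8. Two eyes, no fallback.** A subject random intercept plus an eye-level unstructured matrix, Months 6–24, all subjects bilateral, slope correlation 0.5–0.8: about 10–14%.

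**9. Other growth shapes.** Under pure random-walk growth, with s from 0.05 to 0.8 and baseline rows kept, AR(1) gives 6–11% and CS 18–22%.

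**The case against.** The strongest reply is that the plan may never reach AR(1) or CS. They are fourth and fifth after an unstructured first choice. SAP 4.7 leaves no change value defined at baseline, and SAP 6.2.2 uses the same five-visit list for a categorical-time model. Read that way, with one eye per subject, the unstructured fit is close to 5%. This stands. It limits how likely the problem is, but not its size if the fallback is used.

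A reader might infer that the SAP favours keeping the zero rows, and hence that only AR(1) or CS can be fitted. The documents do not support that. The five-visit list and the baseline-to-Month-24 slope point one way and 4.7 the other. The fallback trigger is non-convergence, which depends on the software. A program that stops at a tiny baseline variance under unstructured returns a standard error near 0.204, which is close to correct. Zero rows therefore do not inflate the error by themselves; the equal-variance structures without a random slope do.

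A reader might also infer that dropping the zero rows breaks the Month 6 knot model. SAP 6.1.4 asks only for the Month 6 to Month 24 output from that model, and the first slope of the Month 12 knot model is identified from Months 6 and 12.

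Finally, the categorical-time Month 24 analysis in 6.1.5.3 gives a useful comparison, but it is a sensitivity analysis and does not replace the primary p-value.

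**Conclusion.** The point holds as a defect in a stated rule for the only primary test. If AR(1) or CS is used as 6.1.3 permits, type I error is about 13–26% with post-baseline rows only and about 19–34% with zero baseline rows kept. Keeping those rows makes the fallback more likely, depending on the program. Where subjects contribute two Eligible Eyes, even the first-choice structure, read as a subject random intercept plus an eye-level unstructured matrix, gives about 10–14% if all are bilateral.

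It would be tempting to quote 19–34% as the trial's error rate. The documents do not fix it. They give no measurement SD, share of two-eye subjects, between-eye correlation or growth shape, and no likelihood of reaching the fallback. The one-eye ranges assume near-linear growth, slope SD 1.2 and s of 0.1–0.5 mm². They rise with two eyes and fall under random-walk growth, to 6–11% for AR(1) with baseline rows kept. This should be fixed before unmasking. Confidence in the direction is high; confidence in the exact size is moderate.

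**What to change.** 1. State in 6.1.3 that only Months 6, 12, 18 and 24 are response records, and that baseline area enters through the change score and as a covariate.
2. Include subject and eye random slopes on time. Alternatively, use an unstructured covariance that covers both eyes of a subject, without separate random intercepts, which would be redundant.
3. Remove AR(1) and CS without a random slope from the fallback list, or require a robust (sandwich) standard error if they are used.
4. Apply the same form to the analyses that reuse this model: the piecewise models in 6.1.4, and the multiple-imputation, per-protocol and other sensitivity analyses in 6.1.5.

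The cost is SAP wording and code; no new data are needed. With post-baseline rows, an unstructured matrix and one eye per subject, calculated power for the planned effect is 78.9–83.6%, so little is lost. Constraining the model through zero and dropping the non-time main effects, or modelling raw area at all five visits, are optional modelling choices and not needed to correct this point.
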